4.2.2 Main Analytical Approach for Primary Endpoint(s)

The endpoint is calculated for each treatment arm as:

% participants with HBsAg loss= (Number of participants with HBsAg loss / Total number of participants) *100

The treatment difference (adjusted for baseline HBsAg stratification level, along with the associated 95% confidence interval) in the proportion of participants with HBsAg loss at 24 weeks post-EOT between the NME treatment arm and control arm will be estimated using Cochran-Mantel-Haenszel (CMH) weighting method with continuity correction [Cochran 1954; Mantel and Haenszel 1959].

The percentage of participants with HBsAg loss will be analyzed using evaluable patients from the mITT population.

4.2.3 Sensitivity Analyses

- A) Following sensitivity analyses for the primary endpoint will be carried out to assess the impact of consecutive missing doses of siRNA
 - Completer Analyses (only include participants who have had full siRNA dosing)
 - All patients (mITT population including 'unevaluable' patients)
- B) Sensitivity analysis will be performed on primary endpoint for the patients who achieve HBsAg loss at the primary endpoint but did not meet the NUC stopping criteria. A non-responder imputation will be implemented for these pts.
- C) Sensitivity analysis may be performed using stratification based on IxRS data if higher number of inconsistencies are observed compare to the actual stratification.

4.2.4 Supplementary Analyses

To evaluate the impact of COVID-19, the ICE associated with the COVID-19 disruptions or other non-safety reason will be handled using a hypothetical approach for the primary endpoint, where the observed data from date of intercurrent event will be set to missing and missing data imputation using Multiple Imputation (MI) will be applied. The aim is to estimate a treatment effect "as if" the ICE had not happened.

Note that the attributes of population, variables and population level summary will remain the same as the primary estimand. The analysis methods will be the same as described for the primary estimand.

Two scenarios will be evaluated -

- Three or more consecutive siRNA doses missing for a patient.
- 2) Two or more consecutive siRNA doses missing for a patient

A free-text response has been mandated in the additional observation page of eCRF if the patient missed doses due to COVID-19 or other non-safety reason. Data flag will be

creating to identify patients with ≥2 and ≥3 siRNA missing doses and observed data from date of intercurrent event will be set to missing. In a case, patients missing doses and discontinued from study at primary timepoints then it will considered as non-responder.

For the purpose of statistical analysis, it is reasonable to assume that these missing data are missing at random (MAR) and the statistical models that require MAR assumption are appropriate.

Markov Chain Monte Carlo (MCMC) will be first applied to augment data into monotonic missing pattern and PROC MI will be used to generate 30 datasets using the regression method. The variables to be included in the imputation model are: treatment group, baseline HBS stratification, Baseline, and measurements at each visit up to the end of the analysis period. The random seed for MCMC and the random seed for PROC MI are specified in Appendix 6. Subjects will be characterized as responders or non-responders based on MI imputed datasets. Using the CMH model adjusted by the stratification factor, the imputed endpoints will be analyzed using each of the 30 datasets. SAS PROC MIANALYZE will be used to generate the final inferences of the risk difference between NME treatment arm and control arm (NUC).

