4.1 GENERAL CONSIDERATIONS

Disposition and protocol deviations listings and summaries will be based on all randomized participants. Analysis of safety will be based on the safety population. Pharmacodynamics and efficacy analysis will be based on the modified intention-to-treat (mITT) population. Pharmacokinetic analysis will be based on PK population. Immunogenicity analysis is based on the immunogenicity population.

For the treatment arms where additional patients have been recruited to proactively mitigate any impact of COVID-19 or force majeure events, the primary analysis will be performed when approximately 30 patients considered evaluable for the primary analysis reach the primary endpoint of Week 24 post EOT. If the primary analysis is positive for an experimental treatment arm, any additional patients that have been recruited to that treatment arm, will continue and be included in the final CSR.

Evaluable patients: A patient from the mITT population will be considered 'evaluable' if no more than two consecutive siRNA missing doses due to non-safety reasons (e.g., COVID-19 disruptions). This is based on the siRNA liver half-life of ~10 weeks.

estimated from ph1 data. Therefore, after two consecutive missing doses the drug left in the liver is expected to be \sim 40%, which was considered adequate as patients would restart dosing so up to 2 missing doses are not expected to have a major impact on the efficacy.

Evaluable patients in mITT population will be used to estimate the primary endpoint/estimand.

Any subject who does not have a virology parameter evaluation during the pre-specified window for 24-week Follow-up visit (either due to missing assessment or due to early withdrawal from the study or study treatment) will be considered as a non-responder. However, if the subject with missing evaluation is a responder both before and after the visit window, then the subject will be categorized as a responder for that visit.

Key definitions:

The following definitions will be used:

Baseline: The baseline value is defined as the last available valid (quantifiable continuous or categorical value), non-missing observation for each participant prior to first study drug administration. Repeat and unscheduled assessments will be included in the derivation of the baseline values.

HBsAq Loss: HBsAg loss refers to a negative/undetectable HBsAg level, HBsAg loss is defined HBsAg levels <0.05 IU/mL.

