4.2 PRIMARY ENDPOINTS/ESTIMANDS ANALYSES

4.2.1 Definition of Primary Endpoint(s)/Estimand(s)

Definition of Primary Endpoint:

The primary endpoint is HBsAg loss (qHBsAg <0.05 IU/mL) at week 24 post EOT.

The primary endpoint is calculated for each treatment arm as:

% participants with HBsAg loss= (Number of participants with HBsAg loss / total number of participants) *100

The percentage of participants with HBsAg loss will analyzed using evaluable patients from the mITT population.

Definition of Primary Estimand:

In line with the Estimands addendum to ICH E9, the primary efficacy estimand is defined as follows-

The difference between proportions of HBsAg loss (qHBsAg <0.05 IU/mL) at week 24 follow-up in virologically suppressed adult CHB participants on established NUC therapy, with preserved liver function and without significant fibrosis/cirrhosis, treated with

^{**} Evaluate numerical and longitudinal data to understand the discrepancy.

^{***} Depending on numerical values, these may be rare cases of double positive (HBsAg and anti-HBs) usually seen from baseline. Seroconversion will need to be interpreted using longitudinal data.

combination therapy* versus NUC, irrespective of adherence to IMP or whether prohibited medication and/or food has been taken.

*treatment and dose levels will vary depending on the combination arm and are specified in the relevant arm specific appendix.

The primary efficacy estimand is described by the following five attributes:

- a) **Population**: Evaluable patients from the mITT population as defined in section 3. These will be CHB adult participants who are virologically suppressed for more than 6 months on established NUC therapy as defined by the inclusion and exclusion criteria listed in Protocol WV41073 section 5.
- **b) Primary Endpoint**: % participants with HBsAg loss (qHBsAg <0.05 IU/ml) at 24 weeks post-EOT.
- c) Population level summary: The difference between proportions of HBsAg loss (qHBsAg <0.05 IU/mL) between NME combination over the control arm at week 24 post-EOT
- **d)** Treatment conditions: Treatment and dose levels will vary depending on combination arms and are specified in the relevant arm specific appendix.
- e) Intercurrent Event (ICE):

Table 5 Intercurrent Events Impacting Primary Analyses:

Intercurrent Events	SDR/ NSDR	Estimand Approach
Participants with dose interruptions or switching dose/frequency	SDR	Treatment Policy

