Withdrawal from study treatment due to any medical condition or AEs/laboratory abnormalities	SDR	Treatment Policy
Investigator or Sponsor determines that treatment discontinuation is in the best interest of the participant.	SDR	Treatment Policy
Withdrawal from study treatment due to participant's withdrawal of consent, pregnancy, non- compliance with study requirement, or lost to follow-up	NSDR	Treatment Policy
Participants who take prohibited medication and food and continue in the study (List of prohibited	SDR	Treatment Policy

medication and food provided in Table 4)		
COVID-19 related ICE A) Systematic disruptions: i) Discontinued study treatment due to covid19 disruptions ii) Discontinued study due to covid19 disruptions iii) Study treatment interruption due to covid19 disruptions iv) Missed dose(s) with potentially major impact on the efficacy due to covid19	NSDR	Treatment Policy
B) COVID-19 infection related ICEs; i) Covid19 infection and concomitant medication ii) Use of the prohibited medicine or therapy iii) Death due to covid19		
Patients who met the NUC d/c criteria at EOT (or in the follow-up period) but did not stop NUC.	SDR	Treatment Policy

SDR- Study Drug Related, NSDR- Non study drug related

A "treatment-policy strategy" will be used accounting for each type of intercurrent event (ICE) as mentioned above. "treatment-policy strategy" where all observed values will be used regardless of the intercurrent event.

Table 6 List of prohibited medication and food

List of prohibited medication-

Systemic immunosuppressive drugs, immunomodulators, cytotoxic or chemotherapeutic agents, radiation therapy.

Systemic high-dose corticosteroids (e.g. >40 mg prednisolone per day) > 7 days or low-dose corticosteroids (e.g. >20 mg prednisolone per day) for > 14 days.

Arm specific prohibited medications

Prohibited food:

For CpAM, any nutrients have been taken during study which modulate activity of CYP enzymes (e.g., grapefruit-, apple-, or Seville orange-containing products).

For TLR7(3), consumption of green tea beverages during the treatment period.

CHB participants who routinely take herbal medicines which may have immunemodulatory effects

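### The COVID-19 hypothetical analysis keeps a population that contains essentially none of its Scenario 1 patients, and its handling of HBsAg at the 0.05 limit pulls imputed participants towards non-response

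*SAP*

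**What the plan says.** SAP 4.2.4 handles COVID-19 and other non-safety disruptions by a hypothetical strategy. Data from the event onward are deleted and multiply imputed. The section states: "Note that the attributes of population, variables and population level summary will remain the same as the primary estimand". Scenario 1 is "Three or more consecutive siRNA doses missing for a patient"; Scenario 2 is two or more. The data flag is described as "creating to identify patients with ≥2 and ≥3 siRNA missing doses", without repeating that the doses must be consecutive. One exception is given: "patients missing doses and discontinued from study at primary timepoints then it will considered as non-responder".

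The primary estimand's population in SAP 4.2.1 is "Evaluable patients from the mITT population as defined in section 3". SAP 4.1 defines evaluable: "A patient from the mITT population will be considered 'evaluable' if no more than two consecutive siRNA missing doses due to non-safety reasons". Table 5 nevertheless lists "Missed dose(s) with potentially major impact on the efficacy due to covid19" among the intercurrent events. Sensitivity analysis A in SAP 4.2.3 brings back the unevaluable mITT patients, but without the hypothetical strategy.

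For the imputation, SAP 4.3 and Appendix 6 set a result reported as <0.05 to 0.05. Appendix 6 then imputes log10 HBsAg by regression under multivariate normality, back-transforms, and counts an imputed value as a response only if it is below 0.05. It calls this conservative. SAP 4.1 and Appendix 6 also keep a participant as a responder "if the subject with missing evaluation is a responder both before and after the visit window".

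**The concern.** The population sentence and Scenario 1 exclude each other. The patients with the longest dose gaps, for whom the analysis was built, are outside it. Table 5 and the flag for three or more missed doses suggest they were meant to be included, so the population sentence looks like a drafting slip. A programmer would still follow it, and switching to full mITT after seeing data would be a post-hoc choice of population.

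The imputation rule works against the analysis's aim. Responders' stored values sit exactly on the cut-off, so a symmetric normal draw around such a prediction puts half the probability on the wrong side. Only siRNA arms can have the event, so the pull lowers the active response and shrinks the difference. The SAP discloses the direction but not the size.

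**Working it through.** **1. The plan's own figure.** SAP 2.2 gives 78% power for 33% vs 3%, 30 per arm, continuity-corrected two-sided chi-squared test at 5%. Effective n = 30 × (1 − 1/(30 × 0.30))² = 23.7. Power = Φ[(√23.7 × 0.30 − 1.96 × √(2 × 0.18 × 0.82)) / √(0.03 × 0.97 + 0.33 × 0.67)] = Φ(0.79) = 78.6%. This reproduces the figure, which does not depend on either issue here.

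**2. Population.** Classify patients by their longest run of consecutive non-safety missed siRNA doses:

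| Longest run | Evaluable (4.1) | Scenario 1 event | Scenario 2 event |
|---|---|---|---|
| 0–1 | yes | no | no |
| 2 | yes | no | yes |
| 3 or more | no | yes | yes |

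Scenario 1 within the evaluable set is empty. Scenario 2 within it is a run of exactly two. A run mixing safety and non-safety misses is an edge case, hence *essentially* none. SAP 1.2 reports 30–53% of participants per arm with missed visits and siRNA doses, about 9 to 16 of 30. It does not say how many had runs of two or three.

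**3. A participant predicted exactly at the limit.** The share called a responder is Φ(0) = 50% at any residual SD. Appendix 6 back-transforms to the precision of the observed data; if that is two decimals (an assumption), the share is Φ(log10(0.045/0.05)/SD). Relaxing the rule to ≤0.05 after such rounding gives Φ(log10(0.055/0.05)/SD).

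| Residual SD (log10) | <0.05 after rounding | ≤0.05 after rounding |
|---|---|---|
| 0.15 | 38% | 61% |
| 0.3 | 44% | 55% |
| 0.5 | 46% | 53% |
| 0.8 | 48% | 52% |

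**4. Whole distribution, closed form.** Let latent log10 HBsAg be normal with SD 1 and mean μ above the limit, so true response is Φ(−μ). After flooring, the mean is m = μΦ(μ) + φ(μ) and the second moment is (μ² + 1)Φ(μ) + μφ(μ). A normal fitted to these moments puts Φ(−m/s) below the limit, where s is the floored SD. At 33% true response, μ = 0.44, m = 0.657 and s = 0.726, so the imputed share is 18.3%. Likewise 50% becomes 24.7%, 20% becomes 12.6% and 3% becomes 2.6%.

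**5. Effect on the difference (simulation).** Assumptions: 30 per arm, 12 with baseline below 1000 IU/mL; visits at Weeks 12, 24, 36 and 48 and follow-up Weeks 12 and 24; active response in the low/high stratum of 50/20%, 28/10% or 15/4%; control 3%; responders 0.7 log10 below the limit from EOT; active non-responders falling by a mean 1.9 log10, then partly rebounding; within-person noise 0.1, 0.3 or 0.5 log10. Three or 6 random active participants lose all data from Week 24, Week 36 or EOT onward; no control is imputed. That makes 54 settings, each with 400 trials and 15 imputations (Monte Carlo SE at most 0.2 points). Bias is the CMH-weighted difference after imputation minus that in the undeleted data.

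| True difference (points) | Points lost, 3 of 30 imputed | Points lost, 6 of 30 imputed |
|---|---|---|
| 26–30 | 1.9–2.7 | 4.1–5.1 |
| 13–15 | 1.1–1.6 | 2.1–3.0 |
| about 5 | 0.4–0.8 | 1.2–1.5 |

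For scale, one participant is 1/30 = 3.3 points. An unadjusted Wald 95% interval at 33% vs 3% is ±1.96 × √(0.33 × 0.67/30 + 0.03 × 0.97/30) = ±18 points. Calling all 6 imputed participants non-responders would lose 5.8–6.8 points at 26–30.

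A separate simulation with other trajectories and 6 of 30 imputed lost 2.8–4.9 points at true differences of 22–29 and 2.0–2.8 at 10–14.

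**6. Alternatives.** The ≤0.05 rule after rounding still loses 4.0–5.0 points with 6 of 30 at 26–30. Predictive mean matching (5 donors) with 0.05 counted as loss gave a bias of −0.5 to +1.1 points over all 54 settings.

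**The case against.** The cut-off itself matches the endpoint definition, and relaxing it to ≤0.05 barely helps. The driver is therefore the floor at 0.05 combined with an untruncated normal model, not the inequality sign. That stands, and the remedy must target the combination. The 50% figure follows from symmetry and describes only participants predicted exactly at the limit. That also stands; the closed form and the simulation are what speak to imputed participants in general.

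The sizes rest on inputs the documents do not give: the number imputed, the trajectories, the residual spread, and which missed dose dates the event. Predictive mean matching can also err slightly upwards. These points limit the precision of the size, but no setting run under any of the assumed trajectories reversed the direction.

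Two SAP rules limit the reach. Study discontinuers with missed doses count as non-responders, which lowers the number imputed. The before-and-after exception protects responders who miss only the Week 24 visit and have a later result, but not those whose data are deleted from the event onward. Finally, this is a supplementary analysis in an exploratory study without formal testing, and the SAP discloses the direction. That argues for moderate priority. It does not resolve the population conflict, which needs no assumptions.

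**Conclusion.** Both parts hold. The population conflict is a matter of definitions: as written, Scenario 1 has essentially no patients with its event and Scenario 2 only those with runs of exactly two. The downward pull from the imputation is certain in mechanism and was consistent in every setting run. Its size is illustrative: about 2 to 5 points with 3 to 6 of 30 imputed at a true difference of 26 to 30, and less at smaller differences. That is milder than calling every imputed participant a non-responder, but goes most of the way. The primary analysis is not affected, and no interim or expansion rule uses this analysis. It should be corrected, because this is the only planned analysis that estimates the effect without the disruption.

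**What to change.** In SAP 4.2.4, run both scenarios on the full mITT population, including unevaluable patients, and make the data flag require consecutive missed doses. The natural comparator is then the all-patients analysis in 4.2.3 A, because the population also differs from that of the primary analysis.

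In Appendix 6, use an imputation that can return the limit value and count that value as loss, for example predictive mean matching with 0.05 counted as loss. Classify before rounding. State that observed values keep their observed response status; this is a precaution, since an observed loss stored as 0.05 would fail a re-derived test of being below 0.05. Report the number imputed per arm and scenario.

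The cost is a few SAP sentences and minor re-programming, with no new data.

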2.2 SAMPLE SIZE DETERMINATION

Approximately 30 participants will be randomized in each treatment arm. Approximately five replacement participants per arm may be replaced if participants have a dose regimen change or discontinue due to non-safety reasons. This is to ensure that the number of participants per arm of the randomized dose regimen remains close to 30.

In the event of COVID-19 or force majeure events that significantly impact compliance with the randomized dosing regimen, up to 30 additional participants may be enrolled per treatment arm to ensure that the randomized dose regimen remains close to 30. Criteria and the decision to enroll additional participants will be at the Sponsor's discretion.

The overall number of participants in this study will depend on the number of treatment arms that are included, which is not known at present.

The primary endpoint is the proportion of participants with HBsAg loss at 24 weeks post-EOT. Assuming a 3% NUC response rate, a sample size of 30 participants per arm provides 78% power to detect a pairwise 30% difference between a combination treatment arm and the NUC control arm. This is based on a two-treatment arm continuity corrected, two-sided, chi-squared test of equal proportions at a significance level of 5 %.

The sample size of combination treatment arms that achieve 30% delta for HBsAg loss at Week 48 (EOT) or follow-up Week 12 or 24 may be expanded up to approximately 100 participants. An expansion may also be triggered prior to EOT, for a treatment arm that gives an early indication of efficacy. The decision criteria to trigger an expansion arm in this case, will be documented as an appendix to the IMC/SOC charter. The expansion arm may be utilized to increase the precision of the efficacy treatment estimates; exploration of participant subgroups (e.g., baseline HBeAg status) and/or to gain additional safety data prior to Phase 3 clinical trials.

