Repetition of imputations, K, must be determined in advance. In the usual clinical settings expecting less than 30% missing information, K=30 repetitions are deemed sufficient. When missingness exceeds 30%, depending on the power falloff tolerance level, number of repetitions may need to be increased. It is suggested that the number of repetitions (K) should be at least equal to the percentage of missing.

Derivation of Response Status and Non-Responder Imputation.

For each 'complete' dataset, the imputed post-baseline values will be back transformed to the original scale of the same precision as the observed data. Response status will be determined accordingly.

The imputed response status for missing due to reasons other than COVID-19 will be overridden by non-responder imputation to ensure that multiple imputation is only applied to missing due to COVID-19 and due to hypothetical strategy.

The only exception is that a subject will be categorized as a responder for the visit if the subject is a responder both before and after the specified visit window.

Analysis:

The statistical analysis will use the Cochran-Mantel-Haenszel (CMH) test adjusted by the stratification factors.

Also, binomial proportion and exact confidence interval for a proportion will be calculated for each treatment arm.

Analysis of Each Dataset

Combination Therapies for CHB—F. Hoffmann-La Roche Ltd Statistical Analysis Plan WV41073

For each of the K 'complete' datasets, the CMH test will be used to estimate the NME difference versus control and the corresponding standard error.

Also, for each of the K 'complete' datasets, binomial proportion and exact confidence interval for proportions will be calculated for each NME and control arm and the corresponding standard error.

Synthesis of Results for Statistical Inference

The results from the K 'complete' datasets will be synthesized using the SAS procedure PROC MIANALYZE, following Rubin's formula to derive the MI estimator of the treatment difference and proportions for the final inferences.

6. REFERENCES

Evolution of the food and drug administration approach to liver safety assessment for new drugs: current status and challenges [John R Senior, 2014]

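### The COVID-19 hypothetical analysis in SAP 4.2.4 counts participants who left because of COVID-19 as non-responders, against its own aim and against SAP Appendix 6

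*SAP*

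**What the plan says.** SAP 4.2.4 (Supplementary Analyses) applies a hypothetical strategy to intercurrent events from COVID-19 disruption or another non-safety reason, "where the observed data from date of intercurrent event will be set to missing and missing data imputation using Multiple Imputation (MI) will be applied". Its purpose is explicit: "The aim is to estimate a treatment effect" as though the event had not occurred. Two scenarios are run, for three or more and for two or more consecutive missed siRNA doses. The population stays that of the primary estimand.

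The same section then gives a rule for leavers: "patients missing doses and discontinued from study at primary timepoints then it will considered as non-responder". It does not distinguish reasons for leaving.

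Two other places bear on this:

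- SAP 4.2.1, Table 5, lists "Discontinued study due to covid19 disruptions" among the COVID-19 intercurrent events.
- SAP Appendix 6 (Section 5.6), under the derivation of response status, says: "The imputed response status for missing due to reasons other than COVID-19 will be overridden by non-responder imputation". It gives the purpose as confining MI to values missing through COVID-19 or through the hypothetical strategy.

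SAP 4.2.4 refers to Appendix 6 for its random seeds, so both texts govern the same run.

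**The concern.** A participant who missed siRNA doses and then left the study because of COVID-19 disruption is fixed at non-response by SAP 4.2.4 and imputed by Appendix 6. A programmer cannot follow both.

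The 4.2.4 rule also works against the question being asked. Leaving because of COVID-19 is part of the disruption that the analysis is meant to remove, yet it is scored as treatment failure. A participant with the same dosing gap who stayed has later data deleted and imputed.

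What is at stake is whether this analysis says anything about these leavers beyond the primary analysis, and whether the choice between the two rules is made before results are seen.

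**Working it through.** **1. The two rules side by side, for a participant with a flagged siRNA dosing gap**

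| Participant | SAP 4.2.4 | Appendix 6 | Agree? |
|---|---|---|---|
| Stayed in the study | MI | MI | Yes |
| Left because of COVID-19 disruption | Non-responder | MI | No |
| Left for a reason unrelated to COVID-19 or to the gap | Non-responder | Non-responder | Yes |
| Left for another non-safety reason covered by the strategy | Non-responder | Unclear: the override catches causes other than COVID-19, but the stated purpose gives MI to values missing through the strategy | Unresolved |

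The clear contradiction is the second row.

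**2. Comparison with the primary analysis.** SAP 4.1 counts a missing follow-up Week 24 value as non-response, including after early withdrawal. Its one exception needs a response both before and after the visit window, which someone already out of the study cannot show. For COVID-19 leavers the 4.2.4 rule therefore gives the same value as the primary analysis.

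**3. Direction relative to MI.** MI gives a participant a response probability of at least 0, and the rule fixes it at 0. So the arm's rate falls or stays the same. The flags count siRNA doses, and the control arm (SAP Appendix 1) receives only background NUC, so the change falls on the siRNA arms.

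**4. The planning rate.** SAP 2.2: "Assuming a 3% NUC response rate, a sample size of 30 participants per arm provides 78% power to detect a pairwise 30% difference", using a "continuity corrected, two-sided, chi-squared test of equal proportions at a significance level of 5" percent. The implied combination-arm rate is 3% + 30 points = 33%. To check that reading, invert the Fleiss continuity-corrected formula with n = 30 and d = 0.30:

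- Effective n = (2nd − 2)² / (4nd²) = 16² / 10.8 = 23.70
- z = [√23.70 × 0.30 − 1.96 × √(2 × 0.18 × 0.82)] / √(0.03 × 0.97 + 0.33 × 0.67) = (1.461 − 1.065) / 0.500 = 0.79
- Power = 78.6%, against the stated 78%. The figure reproduces, so 33% is the design rate.

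**5. Illustrative size.** Suppose MI would have given each affected leaver the planning rate. With m such participants in an arm of 30, the loss in treatment difference is (m / 30) × 33 points:

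- m = 1: 1.1 points (30.0 to 28.9)
- m = 3: 3.3 points (30.0 to 26.7)
- m = 5: 5.5 points (30.0 to 24.5)

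The values of m are assumptions; the documents give no count.

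**6. Who can be affected.** SAP 4.1 defines evaluable participants as having at most two consecutive siRNA doses missed for non-safety reasons, and 4.2.4 keeps that population. Read literally, the scenario of three or more missed doses is then empty for non-safety gaps. In the other scenario the rule reaches people with exactly two consecutive missed doses who then left. If doses due after departure count as missed, these are mainly people who left late in treatment or during follow-up.

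**The case against.** The strongest case on the other side is that this is loose wording in one supplementary analysis of an exploratory study. There is no formal hypothesis testing (SAP 2.1), and the interim expansion and new-arm criteria use observed HBsAg loss rates rather than this output (SAP 4.7.1). SAP 4.2.3 already plans a completer analysis and an all-mITT analysis. The leaver sentence could be read as an ordinary missing-data rule matching SAP 4.1, and for departures unrelated to COVID-19 it agrees with Appendix 6. Table 5 describes events for the primary estimand, all handled by treatment policy, whereas the 4.2.4 scenarios are defined by missed doses.

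Much of that limits the weight of the point. It does not remove the conflict, because Appendix 6 is written for this imputation and directs COVID-19 missingness to MI. Nor does a conservative label answer it: an analysis meant to differ from the primary for these people gives the same value.

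The objection does rule out several stronger readings:

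- A reader might infer that the most severely disrupted participants are scored as failures. On the stated population, those with three or more consecutive non-safety missed doses are excluded, not scored.
- A reader might infer that the sentence lowers the siRNA arms outright. That holds only against MI; against the primary analysis nothing moves.
- A reader might infer that the sentence makes the comparison one-sided. The one-sidedness comes from flagging siRNA doses only, and would remain if the sentence were corrected.
- A reader might take the 30–53% per arm in SAP 1.2 as the scale. It counts missed visits and siRNA administration, not people with consecutive missed doses who also left.

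**Conclusion.** The point holds for participants who left the study because of COVID-19 disruption. For them SAP 4.2.4 defeats its stated aim, contradicts Appendix 6 and reproduces the primary non-responder result. The rule for departures caused by other non-safety gaps is unresolved between the two sections.

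Relative to MI, the direction is certain: the siRNA-arm rate is lower or unchanged. The size is not known. The figure of 1.1 points per participant assumes an arm of 30 and an imputed response probability of 33%. MI conditions on stratum, baseline and visit values, so an individual's probability could be well away from that. The evaluable-population restriction probably keeps the number small. This is a modest correction, worth making before the analysis is run; it does not undermine the primary analysis.

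**What to change.** In SAP 4.2.4, restrict the non-responder sentence to participants who discontinued the study for reasons other than COVID-19 disruption, and state that COVID-19-related discontinuers are imputed by MI as in Appendix 6.

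In both sections, state the same treatment for discontinuation due to the other non-safety gap reasons that the hypothetical strategy covers. Appendix 6 does not settle this as written, so it needs a decision and not just a cross-reference. The present rule can be kept as a labelled worst-case run.

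The cost is a small text change in two SAP sections and a little extra analysis work. The reasons needed are already planned for collection: the primary reason for study withdrawal goes on the eCRF (Protocol 7.2), and the reason for missed doses is captured as free text (SAP 4.2.4), which will need coding. The downside is that results for the imputed leavers rest on the missing-at-random assumption that 4.2.4 already makes for the other imputed values; the worst-case run would show how much depends on it.
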